$$[\lambda_{\text{lower}}, \lambda_{\text{upper}}] = [\{0.5 \chi^2(\alpha/2; 2x)\}/n, \{0.5 \chi^2(1-\alpha/2; 2x+2)\}/n],$$

where $\chi^2(\gamma, r)$ is the 100 γ th percentile of a chi-square distribution with r degrees of freedom, n is the patient years under risk for the event, x is the number of patients with event, and α for (1- α) % 2-sided CIs.

Cumulative risk is defined as cumulative proportion of patients with event and will be calculated as the Kaplan-Meier estimate for failure. The Kaplan-Meier curve will be plotted. The proportion of patients with event, as well as the proportion of censored patients falling into specified intervals and the Kaplan-Meier estimate for failure will be computed for the following categories:

- ≤ 3 months
- $3 < \text{and } \leq 6$ months
- $6 < \text{and } \leq 12$ months
- $12 < \text{and } \leq 18$ months
- $18 < \text{and } \leq 24$ months
- $24 < \text{and } \leq 30$ months
- > 30 months

In the following if not stated otherwise for all analyses only patients from the restricted patient set are considered. Furthermore only the first treatment period is included (i.e. as-treated analysis) if not mentioned otherwise (like e.g. for ITT analyses).

- 1) Main analysis of composite outcome (Stroke, systemic embolism, myocardial infarction, life-threatening bleeding events and vascular death)

Acknowledging the limited precision given the sample size and the potential limitations, for the main comparison of the two treatment groups, Dabigatran and VKA, with regards to the composite outcome a multivariable Cox regression model (according to the 1160.129 and 1160.136 protocols) will be performed if those patient groups are determined to be comparable in terms of the PS analysis. The multivariable Cox regression model will include the following variables as core variables: treatment, age (<65 , $65-75$, >75), gender and the following main stroke and bleeding risk factors: prior bleed, previous stroke/TIA, previous myocardial infarction, abnormal kidney function and concomitant antiplatelets use. The following further covariates will be investigated within a model selection procedure: (sub)region, congestive heart failure, left ventricular

hypertrophy, systemic embolism, complex aortic plaque, hypertension, diabetes mellitus, PAD, CrCl, NSAID use type of AF, hepatic disease, alcohol abuse, any drug (HAS-BLED), previous OAC use (within 3 months), smoking status, and concomitant medication like antipsychotics.

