The correlation of covariates will be assessed and in case of a high correlation between two or more covariates the exclusion of at least one covariate might need to be discussed. Exclusion of covariates with high proportion of missing values might be considered.

The further covariates selection procedure will start with the baseline model including all core variables and will add only one of the further variables at a time. Only the variable which has the largest effect on the treatment estimate will be included in the next step model and only if the treatment effect estimate (hazard ratio) is relatively changed by more than 10% in comparison to the model with the core variables only. This step is repeated on the new model until none of the other variables change the treatment effect estimate by more than 10% in comparison to the resulting model from the previous step. To account for model overfitting, another restriction will be the number of events in comparison to the number of degrees of freedom required to represent all of the variables in the model. For example, a three-level categorical variable would require two degrees of freedom. The number of degrees of freedom for all variables*10 shall not exceed the number of events reported for the composite outcome. For example if 200 events are reported for an outcome, than the number of degrees of freedom summing up over all covariates included in the model is not allowed to exceed 20. If so the last covariate resulting from the last step of the model selection procedure process which was about to be included in the main model needs to be excluded from the final model and the selection process is stopped and the previous model resulting from the previous step is checked in the same way. Generally the selection procedure will be stopped as soon as the number of degrees of freedom for all covariates in the model multiplied by 10 exceeds the number of events.

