- j. The main analysis might be repeated using a different composite outcome definition: replacing vascular death with all cause death in the composite outcome
- k. One more sensitivity analysis might be performed by repeating the main analysis using different definitions of washout and gap for treatment discontinuation

3) Analyses of other outcome events

The following Cox models will only be performed if enough events are reported such that the number of events is roughly proportional to the number of degrees of freedom for all the covariates included in the Cox model. If for other kind of outcome events not listed below

enough events are reported a similar kind of analysis might be performed. The same model selection procedure approach as used for the composite outcome will be used. For all models below the following rule of thumb applies as in the main model used for the composite outcome. The number of degrees of freedom for all covariates in the model * 10 roughly shall not exceed the number of events reported for the composite outcome. The PS matched pair analysis on the specific outcome event might be performed for all outcomes. Additional sensitivity analyses for the single outcome events similar to the ones described for the composite outcome under 2) a),c),f) will be performed if the number of events reported is large enough and additional above mentioned sensitivity analysis will be considered.

- *Composite vascular outcome*

Using the same methods as described above for the composite outcome under 1), VKA and Dabigatran treated patients will be compared in terms of the vascular composite outcome using the same approach for the main analysis and the same sensitivity analyses a), c), f), and i) as outlined for the composite outcome above. Additional above mentioned sensitivity analysis might be considered.

- *Stroke/SEE (optional)*

For stroke/SEE events the multivariable Cox model will include the following variables as core variables as used for the composite outcome: treatment, age (<65, 65-<75, >=75), gender and stroke and bleeding risk factors: prior bleed, previous stroke/TIA, previous myocardial infarction, abnormal kidney function, and concomitant antiplatelet use.

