Further covariates will be selected within the model selection procedure: (sub)region, congestive heart failure, left ventricular hypertrophy, systemic embolism, complex aortic plaque, hypertension, diabetes mellitus, PAD, CrCl, NSAID use (including missing/unknown as a separate category), type of AF, complex aortic plaque, hepatic disease, alcohol abuse, any drug (HAS-BLED), smoking status, concomitant medication like antipsychotics, previous OAC use (within 3 months).

A similar model might be run on stroke events alone if the number of events reported is large enough.

- *Major Bleeding*

For the major bleeding outcome event the multivariable Cox model will include the following variables as core variables: treatment, age (<65, 65-<75, >=75), gender and the following bleeding risk factors: prior bleed, abnormal kidney function, any drug-HAS-BLED, and concomitant antiplatelet use. Further covariates will be selected within a model selection procedure: (sub)region, congestive heart failure, previous stroke/TIA, previous myocardial infarction, left ventricular hypertrophy, systemic embolism, complex aortic plaque, hypertension, diabetes mellitus, PAD, CrCl, NSAID use (including missing/unknown as a separate category), type of AF, complex aortic plaque, hepatic disease, alcohol

abuse, smoking status, concomitant medication like antipsychotics, previous OAC use (within 3 months).

- *All Cause Death (optional)*

For death events the multivariable Cox model will include the following variables as core variables like used for the composite outcome: treatment, age (<65, 65-<75, >=75), gender and the following main stroke and bleeding risk factors: prior bleed, previous stroke/TIA, previous myocardial infarction, abnormal kidney function and concomitant antiplatelets use. Further covariates will be selected within a model selection procedure: (sub)region, congestive heart failure, left ventricular hypertrophy, systemic embolism, complex aortic plaque, hypertension, diabetes mellitus, PAD, CrCl, NSAID use (including missing/unknown as a separate category), type of AF, complex aortic plaque, hepatic disease, alcohol abuse, any drug (HAS-BLED), smoking status, concomitant medication like antipsychotics, previous OAC use (within 3 months).

- *Myocardial Infarction (optional)*

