For MI events the multivariable Cox model will include the following variables as core variables: treatment, age (<65, 65-<75, >=75), gender and the following MI risk factors (hypertension, diabetes mellitus, previous myocardial infarction) and concomitant antiplatelet use. Further covariates will be selected within a model selection procedure: (sub)region, left ventricular hypertrophy, systemic embolism, complex aortic plaque, congestive heart failure, PAD, CrCl, NSAID use (including missing/unknown as a separate category), type of AF, complex aortic plaque, hepatic disease, alcohol abuse, any drug (HAS-BLED), smoking status, concomitant medication like antipsychotics, previous OAC use (within 3 months).

If sample size allows, comparisons of other outcomes may be considered for either 1160.129 or 1160.136, if needed.

Dependent on the number of patients receiving different antithrombotic treatment for stroke prevention and dependent on comparability of important baseline characteristics, other pairwise comparisons of the treatment regimes regarding outcome events might be performed similar to the analysis as outlined for Dabigatran and VKA if the total number of events does allow for a meaningful comparison.

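### The main composite Cox model adjusts for age only in three wide bands, which can leave age confounding in the dabigatran v VKA hazard ratio; a pre-specified continuous term would reduce it within the same degrees-of-freedom budget

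*SAP*

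**What the plan says.** SAP 7.6, item 1, sets the core variables of the main composite model: "The multivariable Cox regression model will include the following variables as core variables: treatment, age" (<65, 65-75, >75), then gender, prior bleed, previous stroke/TIA, previous MI, abnormal kidney function and antiplatelet use. Core variables are fixed. The change-in-estimate procedure works only on a further list, which does not contain age.

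Item 3 covers the other outcomes:
- Stroke/SEE (optional): the model "will include the following variables as core variables as used for the composite outcome", then "treatment, age (<65, 65-<75, >=75), gender and stroke and bleeding risk factors".
- All-cause death (optional): "core variables like used for the composite outcome: treatment, age (<65, 65-<75, >=75), gender".
- Major bleeding, with its own core list: "treatment, age (<65, 65-<75, >=75), gender and the following bleeding risk factors".
- MI (optional), with its own core list: "treatment, age (<65, 65-<75, >=75), gender and the following MI risk factors".
- Vascular composite: no bands are printed. It is analysed "using the same approach for the main analysis", so it takes the main model's bands.

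On the model-size cap, the SAP notes that "a three-level categorical variable would require two degrees of freedom", and limits ten times the degrees of freedom to the number of events.

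Of the sensitivity analyses for the composite, 1160.136 keeps only (d), the intention-to-treat version, and (f), the interaction models. Both are built on the main model. The PS-stratified (a) and PS-matched (c) analyses are done for 1160.129 only.

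Protocol 6.2.1 and 6.2.2 collect month and year of birth at baseline in both phases, so age in years is available.

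**The concern.** Treatment is chosen by the physician, and Protocol 3.1 and 3.2.1 name age first among the characteristics to be checked for channelling. Age is also expected to be related to stroke, MI, bleeding and vascular death. A three-level factor removes the between-band part of an age imbalance but not the within-band part. The top band is open-ended, so a 76-year-old and a 92-year-old are treated alike.

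What remains goes into the dabigatran v VKA hazard ratio, and more patients would not shrink it. The rest of the plan does little to catch it:
- Age is fixed, so selection cannot refine it.
- Creatinine clearance, whose formula in Protocol 10.2 contains age, enters only if it moves the hazard ratio by more than 10%. The residual computed below is mostly smaller than that.
- Trimming and the overlap restriction (SAP 7) remove propensity-score tails. They do not balance age among those who remain.

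**Working it through.** **Degrees of freedom.** The plan's own example reproduces: 200 events / 10 = 20 df. Core model by the same counting rule:
- three bands: treatment 1 + age 2 + six binary factors 6 = 9 df, needing 90 events
- linear age: 1 + 1 + 6 = 8 df, needing 80 events
- 3-knot restricted cubic spline: 1 + 2 + 6 = 9 df, needing 90 events
- 4-knot spline: 1 + 3 + 6 = 10 df, needing 100 events

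Linear age saves 1 df, a 3-knot spline is neutral, and a 4-knot spline costs 1.

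**Residual bias: inputs (all assumed).** VKA age is normal with mean 72 and SD 10. Dabigatran patients are d = 1, 2 or 4 years younger with the same SD. Hazard rises by a factor h = 1.5, 2.0 or 2.5 per decade, which is h^0.1 = 1.04, 1.07 or 1.10 per year. The true treatment hazard ratio is 1.

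**Method.** On a grid of single years of age, expected events = person-time × 0.03 × exp[(ln h / 10) × (age − 70)]. A Poisson model with log person-time as offset (the rare-event limit of the Cox model) is fitted to these expected counts with treatment plus each coding of age. There is no simulation noise.

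| d (years) | h per decade | No age term | Main-model bands | Other models' bands | Linear age |
|---|---|---|---|---|---|
| 1 | 1.5 | 0.961 | 0.992 | 0.991 | 1.000 |
| 2 | 2.0 | 0.875 | 0.970 | 0.968 | 1.000 |
| 4 | 2.5 | 0.703 | 0.920 | 0.915 | 1.000 |

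The bands remove most of the confounding and leave 1 − 0.992 = 0.8% to 1 − 0.920 = 8.0%.

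A separate Cox simulation (60,000 patients, 25% attrition per year, 3 years, age mean 71, SD 9.5, hazard ×1.05 to ×1.09 per year, same age differences) agrees. The ratio of banded to continuous-age hazard ratio ran from 0.991 to 0.931.

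**When the age effect is not log-linear.** Let the log hazard be flat below 65 and then rise at 1.5 × ln h / 10 per year:
- Equal SDs, d = 1 to 4, h = 1.5 to 2.5: main-model bands 0.989 to 0.868, linear age 1.000 to 1.001.
- Dabigatran SD 8 or 12, h = 1.5 or 2.0: main-model bands 0.84 to 1.08, linear age 0.967 to 1.03. With SD 12, mean 70 and h = 1.5, linear age gains nothing (1.029 against 1.030).

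Linear age usually reduces the bias but does not always remove it. With unequal spreads the direction can reverse.

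**The band mismatch.** A patient aged 75 is in the middle band of the composite model and the top band of the others. About 3.8% of patients are exactly 75 under the assumed VKA distribution. Switching band sets moves the hazard ratio by 0.0005 to 0.006 in the log-linear scenarios and by at most 0.014 in any scenario tried.

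**The case against.** The documents give no age distribution by treatment, least of all for the restricted set, so every figure above is conditional. The main model is run only if the groups are judged comparable on the propensity score, after trimming and overlap restriction. Kidney function is a core variable. For 1160.129, PS stratification and PS matching, with a 10% standardised-difference check, do not depend on the age bands as covariates. How age enters the propensity score is set in a separate analysis plan that is not available here.

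Precision is also limited. With the SAP's illustrative 200 events split evenly (an assumption), SE(log HR) = √(1/100 + 1/100) = 0.141. The 95% interval is then a factor of exp(±0.277), about 0.76 to 1.32, against a bias of 1% to 8%. No confirmatory testing is planned (Protocol 7.2). A log-linear simulation also favours linear age by construction.

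Much of this stands. The size is unknown and may be small, and 1160.129 has a partial check. Three replies remain. The protocol's main comparability measure is the share of patients in the region of overlap, which does not ensure equal age within it. 1160.136 drops both PS-based analyses. Linear age also held at 1.000 to 1.001 under a non-linear age effect with equal SDs, so the result is not only an artefact of the assumed shape.

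A reader might go further and infer that the differing bands cause the confounding, or that they contradict every other model. The documents do not support either. Both band sets leave nearly the same residual (0.970 and 0.968 in the middle scenario). The vascular composite inherits the main model's bands, and major bleeding and MI have their own core lists. The contradiction is limited to stroke/SEE and all-cause death, both optional.

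**Conclusion.** The point holds as a weakness of covariate coding. Three-band age can leave within-band confounding in the main comparison, and for 1160.136 no planned analysis of the composite adjusts for age in another way. If dabigatran patients are 1 to 4 years younger with equal spread, and hazard rises 1.5- to 2.5-fold per decade, the hazard ratio would be about 1% to 8% too low, in dabigatran's favour. If dabigatran patients are older, the bias would run the other way. The true size depends on the age imbalance left in the restricted set, which the documents do not give.

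It would be too strong to say that continuous age removes the bias: that depends on the functional form, and a linear term left 0.967 to 1.03 when shape and spread both differed. The band mismatch is a separate, minor inconsistency. The text was machine-read, and a lost symbol in the composite's bands could produce it, so it needs checking against the source PDF. If it is a reading error, only that part falls.

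**What to change.** In SAP 7.6, enter age as a continuous core variable in all Cox models, with the form fixed in advance: linear (1 df) or a 3-knot restricted cubic spline (2 df, the same as three bands). Keep the banded model as a sensitivity analysis. Report age by treatment group in the restricted set, so that readers can judge how much the coding matters.

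Separately, check the composite's bands in the source PDF. Use one set for display and subgroups, 65-<75 and >=75, which matches the CHA2DS2-VASc table in Protocol Appendix 10.1.

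The cost is SAP wording plus one extra model run for the sensitivity analysis. No new data are needed, and the df requirement is unchanged or one lower.

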For Phase II a total sample size of 5,000 patients allows an estimation of a population attribute with a precision of less than 2.8% (i.e. width of 95% CI).

For subgroups which consist of at least 500 patients; this allows an estimation of a population attribute within the subgroup with a precision of approximately 8.9% (i.e. width of 95% CI).

For Phase III a total sample size of 10,000 patients allows an estimation of a population attribute with a precision of less than 2.0% (i.e. width of 95% CI).

Estimates for incidence rates (Phase II-III):

Estimates and confidence intervals for incidence rates (interpreted on a descriptive level) will be computed. For Phase II it is estimated to recruit approximately 2,500 patients from EU/EEA member states in the dabigatran treatment cohort whom are followed up for up to 2 years. Assuming a total treatment discontinuation and lost to follow-up rate of 25% per year a

Proprietary confidential information.

© 2014 Boehringer Ingelheim International GmbH or one or more of its affiliated companies. All rights reserved.

This document may not - in full or in part - be passed on, reproduced, published or otherwise used without prior written permission.

total of approximately 3,802 patient-years in patients from EU/EEA member states starting dabigatran will be observed.

When observing 3,802 dabigatran patient years, we will observe at least one patient with an event (ADR, MBE, stroke/SEE, etc), if the underlying incidence rate for this event is 0.079 occurrences per 100 patient years or above with a power of 95%. If we do not observe any event within the 3,802 patient years, it can be excluded with 95% confidence that the underlying true event rate is above 0.079 per 100 patient years in the population.

Based on the recent RE-LY trial (warfarin, dabigatran), it is expected that the incidence rates for stroke/SEE and MBE will be in a range of 1 to 3 per 100 patient years in the total population. The width of the two-sided 95% confidence interval of the population depends on the obtained estimate from the sample of 3,802 patient years; the following table illustrates this relationship:

Table 7.6: 2 95% Confidence intervals based on different scenarios for observed event rates (based on 3,802 patient years)

| Observed event rate per 100 patient years | Lower 95% CI for event rate per 100 patient years | Upper 95% CI for event rate per 100 patient years |
|---|---|---|
| 1 | 0.70773 | 1.372465 |

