| 2 | 1.575877 | 2.503151 |
| 3 | 2.474761 | 3.603743 |

The calculation of confidence intervals is based on the method described in Hahn, Meeker (section 7.2.2; using χ^2 -quantiles). ([R12-3048](#))

As an example, assume that the event rate for stroke per 100 patient years is 1, i.e. we observe ~38 strokes within the 3,802 patient years. The two-sided 95% confidence interval for the population incidence rate per 100 patient years is 0.71 to 1.37. Thus it can be excluded with 95% confidence that the true rate of strokes per 100 patient years is above 1.37 in the population.

For Phase III, for treatment group cohorts which initially consist of at least 2,000 patients, approximately 4,019 patient-years will be observed within the treatment regimen cohort. This approximation is based on the assumptions of a total treatment discontinuation and lost to follow-up rate of 25% per year and an individual follow-up of three years. Therefore, due to the longer individual follow-up in Phase III and thereby the longer observation time per patient, estimates of incidences based on treatment regimen cohorts which initially consist of 2,000 patients will have approximately the same precision as described above (for 2,500 patients in Phase II).

95% confidence intervals will be calculated for several outcome events. Therefore, it can be expected that false positive significant differences may arise, i.e. a treatment regimen cohort may appear by chance with a lower or a higher incidence rate for specific outcome events or for the composite endpoint variable; consequently, results have to be interpreted with care.

Proprietary confidential information.

© 2014 Boehringer Ingelheim International GmbH or one or more of its affiliated companies. All rights reserved.

This document may not - in full or in part - be passed on, reproduced, published or otherwise used without prior written permission.

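### The events-per-degree-of-freedom limit for the single-outcome Cox models counts composite events instead of events of the modelled outcome, so it is too loose for stroke/SEE and MI

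*SAP*

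**What the plan says.** SAP section 7.6, part 1, limits the main composite model to one degree of freedom per 10 composite events. Its illustration begins "For example if 200 events are reported for an outcome, than the number of degrees of freedom" and arrives at a limit of 20. Sensitivity analysis (b) in part 2 repeats the limit, again for the composite.

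Part 3 then covers the vascular composite, stroke/SEE, major bleeding, all-cause death and MI. It has two safeguards.

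- An opening condition: "The following Cox models will only be performed if enough events are reported such that the number of events is roughly proportional" to the model's degrees of freedom. No ratio is given.
- A rule of thumb applied to all the models that follow: degrees of freedom "in the model * 10 roughly shall not exceed the number of events reported for the composite outcome".

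The covariate selection procedure is carried over from part 1. A further covariate enters "only if the treatment effect estimate (hazard ratio) is relatively changed by more than 10" per cent. Stroke/SEE, all-cause death and MI are marked optional; the vascular composite and major bleeding are not.

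**The concern.** The purpose of a limit of this kind is to keep enough events of the modelled outcome behind each estimated coefficient. In parts 1 and 2 the modelled outcome is the composite, so composite events are the right count. In part 3 the same wording is applied to models of other outcomes, and the count no longer matches the model.

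The composite consists of stroke, SEE, MI, life-threatening bleeding and vascular death. Every patient with stroke/SEE, MI or a vascular composite event is therefore already counted in it, and the composite count cannot be smaller than theirs. For these outcomes the literal limit is never stricter than an own-event limit, and it is usually looser. Major bleeding and all-cause death are only partly contained in the composite, so for them the literal limit may be too loose or too strict.

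At stake are the stability of the secondary hazard ratios and the reproducibility of the plan. A stroke/SEE or MI model could pass the SAP's check with well under the 10 events per degree of freedom that the SAP itself sets. Two statisticians could also disagree on whether such a model may be run at all.

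**Working it through.** **Reproducing the documents' figures**

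- SAP example: 200 / 10 = 20 degrees of freedom, as stated.
- Protocol section 7.6 states that for a Phase III cohort of 2,000 patients "approximately 4,019 patient-years will be observed within the treatment regimen cohort", assuming 25% attrition per year over three years: 2,000 x (1 - 0.75^3) / (-ln 0.75) = 4,019, as stated.

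**Relation between the two limits**

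Literal limit = composite events / 10. Own-event limit = outcome events / 10. Before rounding down, their ratio is composite events / outcome events, whatever the cohort size. In the SAP's 200-event example, an outcome with half of the composite events (100; share assumed) supports 10 degrees of freedom, and one with a quarter (50; share assumed) supports 5. The literal rule allows 20 for both, which leaves 5.0 and 2.5 events per degree of freedom.

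**Fixed core variables**

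- Stroke/SEE: treatment 1 + age in three groups 2 + gender 1 + five binary factors 5 = 9. At 10 per degree of freedom this needs 90 events.
- MI: treatment 1 + age 2 + gender 1 + three MI risk factors 3 + antiplatelet use 1 = 8. This needs 80 events.

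**Illustration: two cohorts of 2,000, 2 x 4,019 = 8,038 patient-years**

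This borrows the protocol's precision example and does not forecast the restricted patient set. The protocol expects that "incidence rates for stroke/SEE and MBE will be in a range of 1 to 3 per 100 patient years". The documents give no composite or MI rate, so those rates are assumed. Events = 8,038 x rate / 100, and the limit is events / 10 rounded down.

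| Rate per 100 patient-years | Events | Limit (df) |
|---|---|---|
| 0.5 | 40 | 4 |
| 1 | 80 | 8 |
| 2 | 161 | 16 |
| 3 | 241 | 24 |
| 5 | 402 | 40 |

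- *Stroke/SEE at 1 per 100.* The 80 events support 8 df. The core alone uses 9, giving 80 / 9 = 8.9 events per df. With the composite at 2, 3 or 5 per 100 (assumed), the literal rule allows 16, 24 or 40 df, which is 2, 3 or 5 times the own-event limit. At those limits there are 80/16 = 5.0, 80/24 = 3.3 or 80/40 = 2.0 events per df.
- *Stroke/SEE at 3 per 100.* The own limit is 24. With the composite at 3 to 5 (assumed), the literal limit is 24 to 40, so the excess is 1.0 to 1.7 times.
- *MI at 0.5 to 1 per 100 (assumed).* The 40 to 80 events support 4 to 8 df, against 8 core df.
- *Major bleeding.* At 1 per 100 the own limit is 8, against a literal 16 to 40. At 3 per 100 the own limit is 24, against the same 16 to 40, so the literal rule can also be too strict.

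**Room for the limit to matter**

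The stroke/SEE candidate list has 17 distinct variables (complex aortic plaque appears twice and is counted once). With one extra df for the missing category of NSAID use and one for the three AF types, it uses at least 19 df. Core plus candidates is at least 9 + 19 = 28 df, or 280 events, which is 280 / 8,038 = 3.48 per 100 patient-years. Around or above that composite rate, the literal rule would exclude few or none of the listed covariates.

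**The case against.** The strongest reply is that this is a copied phrase with a sensible reading available. The opening condition of part 3 already ties each model to its own degrees of freedom. The borrowed procedure in part 1 is illustrated with events for an unspecified outcome, and its closing stopping sentence names no outcome. The limit is also a ceiling: each added covariate must move the treatment hazard ratio by more than 10%, in a population already trimmed on the propensity score, and highly correlated or poorly completed covariates may be dropped. Reaching 28 degrees of freedom is therefore unlikely. The models where the direction is certain and the gap may be large are optional, protocol section 7.2 foresees no confirmatory testing, and the size depends on rates that the documents do not give.

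Much of this stands as a limit on weight. A drafting slip is the likely explanation, and the illustration in part 1 does point to an own-event count. It does not remove the defect. The opening condition asks only that the "number of events is roughly proportional to the number of degrees of freedom for all the covariates included in the Cox model", which sets no threshold. The illustration sits inside the composite analysis, whereas the sentence governing part 3 names the composite expressly. The 10% entry rule restrains only the added covariates; the 8 or 9 core degrees of freedom are fixed and can already exceed what the outcome's own events support. Whether a core-only model should run depends on the opening condition, and that is the one without a number. The same sentence also governs major bleeding and the vascular composite, which are not optional.

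**Conclusion.** As written, part 3 of SAP section 7.6 applies its only numeric limit to the wrong event count. For stroke/SEE and MI the direction is certain: the literal limit is equal to or looser than the SAP's own standard of 10 events per degree of freedom. For the vascular composite the direction is the same, but the gap is probably small because only life-threatening bleeds are left out. For major bleeding and all-cause death the error can go either way.

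The size cannot be fixed from the documents. In the illustration the literal limit for stroke/SEE ranges from no excess (3 per 100 patient-years, composite also 3) to five times too many degrees of freedom (1 per 100, composite 5). This rests on two cohorts of 2,000 and an assumed composite rate. SAP section 4 reports that dabigatran uptake was too low to reach the planned group size, and study 1160.136 uses only the EU/EEA and Swiss patients, so own-event counts may be small.

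The main composite analysis is unaffected. The consequence is confined to secondary, descriptive models, but it bears on which of them may be run and with how many covariates. It should be corrected.

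**What to change.** In the rule of thumb in part 3 of SAP section 7.6, replace the reference to composite events with the number of events of the outcome being modelled, in the analysed patient set. State that the opening condition for running a model uses that same count and the same approximate ratio of 10. It can stay a rule of thumb.

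The cost is one phrase and one clause. The rarest outcomes will have fewer covariates or no multivariable model: in round terms, the stroke/SEE core model would need about 90 stroke/SEE events and the MI core model about 80 MI events. Major bleeding or all-cause death could be allowed more covariates if they turn out more frequent than the composite. No new data are needed.
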